3.0 OBJECTIVES & HYPOTHESIS

Primary Objective:

Estimate the efficacy of this regimen as measured by the proportion of subjects who have achieved a complete response (CR) as the best response by the end of therapy.

Secondary Objective:

Estimate the end of treatment overall response rate (ORR).

Exploratory Objective:

Estimate the progression-free survival (PFS), and overall survival (OS) for this combination using the appropriate response criteria for the histology tested. Stratify ORR, CR, PFS, DOR (overall and by type of response), and OS by subjects receiving mosunetuzumab alone vs. mosunetuzumab followed by polatuzumab vedotin and obinutuzumab. Estimate the safety of this regimen as measured by the frequency of adverse events (AEs). Correlate clinical outcomes including but not limited to ctDNA analysis, genomics, cytokine levels.

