Subjects who must permanently discontinue mosunetuzumab monotherapy due to toxicity should have a response assessment with positron emission tomography (PET)/CT as soon as is clinically feasible and be evaluated for consideration of treatment in Part B as outlined below. These subjects would then be realigned to cycle 9 day 1 provided at least 21 days \pm 2 days have passed since the last mosunetuzumab injection

Subjects will undergo a computed tomography (CT) between cycle 4 day 1 and cycle 5 day 1. Those with at least stable disease (SD) or better by Lugano²³ criteria will proceed with treatment for cycles 5-8. Subjects with progressive disease (PD) at this timepoint may proceed with cycles 5-8 if the investigator assesses that the subject is deriving clinical benefit from the study medication (e.g. pseudoprogression). If there is no clinical benefit to this medication seen in patients with PD, subjects should receive additional therapy outside of the protocol.

Imaging with a PET/CT will be performed between cycle 8 day 1 and cycle 9 day 1. Subjects in a complete remission (CR) will not receive any further study therapy and will be observed in long term follow up. For this response assessment, a Deauville score will be assigned by the clinical radiology read. If the sub-investigator or principal investigator disagrees with the Deauville score assigned, another nuclear medicine physician will adjudicate the results.

All other subjects who do not achieve a CR may proceed with Part B of study treatment. Those with progressive disease (PD) may proceed with Part B only if they are deriving clinical benefit from the treatment (e.g., pseudoprogression, mixed response overall reduction in tumor) after discussion with the Principal Investigator.

Mosunetuzumab Dose Modifications/Toxicity Management

Administration of mosunetuzumab will be performed in a clinical setting with immediate access to a code team staff who are trained to monitor for and respond to medical emergencies. Additional management may take place after transfer to the University of Washington Medical Center, where there is access to neurology and nephrology consultation services in the event of cytokine release syndrome and tumor lysis syndrome, respectively.

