- For neutropenia, the ANC should resolve to Grade ≤ 2 or return to $\geq 80\%$ of the baseline value, whichever is lower.
- For increased lab values the abnormality should have resolved to the upper limit of Grade ≤ 1 , or return to $\leq 120\%$ of the baseline value, whichever is higher.

In the event that a patient has a toxicity in Cycle 1 necessitating mosunetuzumab interruption for >7 days, the Principal Investigator should be notified and the patient may be required to repeat mosunetuzumab at the highest dose previously tolerated prior to resuming the planned treatment schedule.

If scheduled dosing coincides with a holiday that precludes dosing, dosing should commence on the nearest following date, with subsequent dosing continuing on a 21-day schedule as applicable.

Patients who discontinue all study treatment for adverse events should continue to have disease assessments per institutional standard of care.

Additional guidance on the management of other risks that may be associated with mosunetuzumab is described in Appendix 14.9 (Neurologic AEs), Appendix 14.10 (Tumor Inflammation or flare), Appendix 14.11 (Neutropenia and thrombocytopenia), Appendix 14.12 (Infections) and Appendix 14.13 (Elevated Liver Enzymes).

Part B

For patients eligible for treatment in Part B, treatment will commence with cycle 9 day 1. This may be delayed for patients who require a washout of an agent listed in appendix 14.4. Cycle length is 21 days. Polatuzumab vedotin will be administered on day 1 of each cycle. Obinutuzumab 1000 mg will be administered (See table 5 and 6 for details on pre-medications and infusion related reaction management) on cycle 9 day 1, day 8, and day 15. From cycle 10 onwards obinutuzumab will only be administered on day 1 (1000 mg). Part B will be administered for 6 total cycles (through cycle 14). A response assessment by CT should be performed after cycle 11, and an end of treatment PET/CT should be performed after cycle 14. Obinutuzumab should be administered prior to polatuzumab vedotin on days that both drugs are administered.

Table 3: Part B dosing table

	Cycle 9			Cycle 10-14
	Day 1	Day 8	Day 15	Day 1
Obinutuzumab IV	1000 mg	1000 mg	1000 mg	1000 mg
Polatuzumab vedotin IV	1.8 mg/kg			1.8 mg/kg

Cycle length = 21 days

Dose Modification

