8.0 STATISTICAL ANALYSIS PLAN: STUDY DESIGN AND STATISTICAL ANALYSIS PLAN

Mosunetuzumab has been extensively studied as monotherapy in the relapsed refractory setting⁶. However, we will have the following safety suspension parameters.

First, any on-treatment death will prompt a suspension of accrual and convention of an ad-hoc safety committee may recommend changes to the protocol and its analysis based on updated information, closure of the protocol, or continued accrual with no modifications.

In addition, we would expect that grade 4 non-hematologic toxicity will be uncommon (< 10%) and is uncommon in standard chemoimmunotherapy. We will suspend accrual until an ad hoc safety committee can be convened to review the event and make recommendations regarding protocol modification or closure if the following criteria are met: If the lower limit of a 95% confidence interval does not include the possibility of this rate being < 10%. Operationally, this would mean if $\geq 5/15$, $\geq 7/30$ or $\geq 9/42$ patients have a grade 4 non-hematologic treatment-related toxicity (excluding CRS as this is evaluated separately).

Grade 2+ CRS is uncommon as well in the relapsed/refractory⁶ as well as untreated setting²¹ and would expect this rate to be < 15%. We will suspend accrual until an ad hoc safety committee can be convened to review the event and make recommendations regarding protocol modification or closure if the following criteria are met: If the lower limit of a 95% confidence interval does not include the possibility of this rate being < 15%. Operationally, this would mean if $\geq 6/15$, $\geq 9/30$ or $11/42$ patients have a grade 2 or higher CRS event.

In addition, this protocol will be monitored by the institutional data safety monitoring committee at regular intervals.

As mosunetuzumab has been extensively studied as monotherapy in the relapsed refractory setting, and obinutuzumab and polatuzumab in combination were not associated with any significant safety concerns (for example, anti-CD20 antibodies can safely be combined with polatuzumab and combination chemotherapy for an equivalent length of time⁷), no specific safety stopping rules will be established. However, this protocol will be monitored by the institutional data safety monitoring committee at regular intervals.

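### The grade 4 toxicity suspension rule pools Part A and Part B, so its sensitivity to Part B toxicity depends on an unstated share of subjects entering Part B

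*Combined protocol and SAP*

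**What the plan says.** Section 8.0 gives the premise, "we would expect that grade 4 non-hematologic toxicity will be uncommon (< 10" per cent), and the criterion, "If the lower limit of a 95% confidence interval does not include the possibility of this rate being < 10" per cent. The working form is that at least 5/15, 7/30 or 9/42 "patients have a grade 4 non-hematologic treatment-related toxicity (excluding CRS as this is evaluated separately"). The consequence is "We will suspend accrual until an ad hoc safety committee can be convened to review the event" and make recommendations. Neither the criterion nor the counts separate Part A from Part B.

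Treatment is sequential (Section 5.3). Subjects in CR after cycle 8 get no further study therapy; "All other subjects who do not achieve a CR may proceed with Part B of study treatment". On timing, "For patients eligible for treatment in Part B, treatment will commence with cycle 9 day 1". Subjects who stop mosunetuzumab for toxicity can be realigned to that visit early, about 21 days after their last injection, if they are not in CR.

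Section 8.0 later argues that the components raised no important safety concerns and says it sets no particular safety stopping rules, although suspension rules stand just above that sentence. Safety is an exploratory aim in Section 3.0: "Estimate the safety of this regimen as measured by the frequency of adverse events (AEs".

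**The concern.** The criterion asks whether the grade 4 rate credibly exceeds 10%. Over all patients, it is tested on a mixture: everyone is exposed to mosunetuzumab, but only some to the Part B pair. A subject who never starts Part B, or has not yet reached it, adds to the denominator and cannot contribute a Part B event. The better Part A works, the fewer subjects enter Part B and the less the rule can register a problem there.

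The documents cite safety data for the components in other settings, not for this pair after a T-cell-engaging antibody. The polatuzumab–obinutuzumab summary in Sections 4.3 and 4.3.1 lists common adverse events without grades, so it gives no grade 4 rate for the pair. At stake is whether an excess of non-fatal grade 4 events in Part B would reach the ad hoc committee through a stated number or only through general oversight.

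**Working it through.** **1. The plan's own thresholds.** The exact one-sided 95% lower limit L solves P(X ≥ x | n, L) = 0.05. The smallest x with L above 10% is:

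- n = 15: 5 (L = 14.2%; 4/15 gives 9.7%)
- n = 30: 7 (11.5%; 6/30 gives 9.1%)
- n = 42: 9 (11.7%; 8/42 gives 9.9%)

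All three match the plan. The same method gives the CRS thresholds of 6/15, 9/30 and 11/42 against 15%. Two-sided exact limits do not fit: 7/30 then has a lower limit of 9.93%. The plan does not name its method; the one-sided exact convention reproduces it.

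**2. Share entering Part B (f).** No share is stated. The only monotherapy CR figures are 41% (Section 4.0) and 43% (Section 4.3), both relapsed/refractory, leaving up to 59% or 57%; 58% is the midpoint. Section 4.0 expects higher CR rates in untreated patients but gives none for Part A. The values 20%, 30% and 40% are assumptions; 20% would need an 80% CR rate from Part A alone.

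**3. Chance that the plan's rule triggers.** Let a be the Part A grade 4 rate and b the Part B rate. The chance that a subject counts as an event is q = a + (1 − a) × f × b. With a = 3% (assumed), b = 30% and f = 20%, q = 0.03 + 0.97 × 0.20 × 0.30 = 0.088. A sequential binomial over the looks at 15, 30 and 42 with complete data gives:

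| Share in Part B | q | Plan's rule triggers, b = 30% |
|---|---|---|
| 20% | 0.088 | 2% |
| 30% | 0.117 | 8% (9% by simulation) |
| 40% | 0.146 | 20% |
| 58% | 0.199 | 52% |

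Varying a from 0% to 5% gives 0.3–5.5% at f = 20%, 2–15% at 30%, 9–30% at 40% and 35–61% at 57%. If everyone received Part B and Part A had no events, the figure would be 93%.

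**4. Timing.** Accrual is 42/30 = 1.4 per month. Cycle 9 day 1 falls 8 × 21 = 168 days (5.5 months) after the first dose for subjects completing Part A. The 15th subject enrols at month 15/1.4 = 10.7, when (10.7 − 5.5) × 1.4, about 7 of 15, are past that date; at the 30th it is about 22 of 30. If looks are taken at enrolment of 15 and 30, simulated detection of a 30% Part B rate falls to 0.1–2% (f = 30%) or 3–13% (f = 57%), for a from 0% to 5%. At 42 no accrual remains to suspend.

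**5. The same criterion on Part B starters.** Smallest x with the one-sided exact limit above 10%: 3/5 (18.9%), 4/10 (15.0%), 5/15 (14.2%), 5/20 (10.4%). One event fewer gives 7.6%, 8.7%, 9.7% and 7.1%. Taking the number of starters as binomial (42, f), with looks at 5, 10, 15 and 20 and complete data:

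| Share in Part B | Triggers, b = 30% | Triggers, b = 10% |
|---|---|---|
| 20% | 22% | 1% |
| 30% | 39% | 2% |
| 40% | 54% | 3% |
| 58% | 76% | 5% |

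**The case against.** A reader might infer that most subjects never receive Part B and that the rule is close to blind to it. The documents do not support this. Their only monotherapy CR figures allow a majority, 57–59%, to enter. At 58% the rule triggers in 52% of trials at a 30% Part B rate and 81% at 40%: weakened, not blind. It is true that nine Part B events cannot occur if only 8 of 42 enter, but that uses an assumed 80% CR from Part A alone; Section 8.0 uses 80% as a benchmark for best response over the whole regimen.

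Nor is Part B unmonitored. Any on-treatment death suspends accrual, the institutional committee reviews adverse events at least annually and as needed (Sections 8.0 and 10.0), and the incidence or severity of adverse drug reactions is a termination criterion (Section 5.9). These stand as safeguards, but none gives a numerical trigger for non-fatal grade 4 events in Part B.

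The sponsor also states a reason for setting no particular stopping rules, in a pilot sized for feasibility. That is a choice, but it rests on component data and sits uneasily with the suspension rules above it.

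Finally, a Part B rule has its own timing limit. The kth starter is expected near month k/(1.4f) + 5.5: the 10th at about month 29 if f = 30%, the 20th at about month 30 if f = 58%. If f = 20%, only about 8 starters are expected in total. This objection stands, and it shrinks the gain available before accrual ends.

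**Conclusion.** The point holds as one of diluted sensitivity. Detection of a Part B rate three times the plan's limit runs from about 2% to 52% as the share entering goes from 20% to 58%, and is lower with looks at enrolment. These figures rest on assumptions outside the documents: a 3% Part A rate, a 30% Part B rate, the shares below 57%, independence between subjects, uniform accrual and, except for the looks at enrolment, complete follow-up at each look. Section 8.0 does not say whether its denominators count enrolled, treated or fully followed patients, or whether the rule is meant for Part A alone; if it is, Part B has no numerical grade 4 rule. The threshold arithmetic is sound. This is an inexpensive improvement to the monitoring, and does not show that the trial is unsafe or its existing rule wrong.

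**What to change.** Keep the overall rule. Add one sentence to Section 8.0 applying the same criterion (one-sided exact 95% lower limit above 10%) to treatment-related grade 4 non-hematologic events with onset in Part B, with subjects who started Part B as the denominator. The triggers are 3 or more of the first 5, 4 or more of the first 10, 5 or more of the first 15, or 5 or more of the first 20. The consequence stays as it is: suspension of accrual pending ad hoc committee review. Name the interval convention, and reconcile the addition with the later statement in Section 8.0 that no particular safety stopping rules are set.

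The cost is that sentence and a count from adverse event data already collected, with no extra patients or procedures. The downside is about a 1–5% chance of an unnecessary committee review if the true Part B rate is 10%. The complete-data detection figures are upper values for what can be gained while accrual is open.

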4.3 Rationale for Mosunetuzumab and Polatuzumab Vedotin with Obinutuzumab in Lymphoma

The most recent data of mosunetuzumab monotherapy in relapsed/refractory indolent NHL demonstrated an ORR and CR rate of 63% and 43% respectively⁶. These patients were examined with step-up dosing (i.e. 0.4/1.0/2.8 – 1.0/2.0/13.5mg, Cycle 1 Day 1/8/15). Grade 2 and 3 cytokine release syndrome was seen in 7.8% and 1.1% of patients, respectively⁶.

The safety and clinical activity of the antibody-drug conjugate polatuzumab vedotin in relapsed/refractory NHL was examined in a phase 1b/2 study¹⁰. Single agent polatuzumab vedotin was associated with objective responses in 23/42 (54.8%) evaluable patients in the dose-expansion cohort (2.4 mg/kg), including 7/42 (16.7%) complete responses (CR). There was an acceptable safety profile at the maximum tolerated dose, with the most common grade 3-4 toxicities being neutropenia (40%), anemia (11%), and peripheral sensory neuropathy (9%). In addition polatuzumab has been safely combined with obinutuzumab in relapsed/refractory follicular lymphoma with an overall response rate of 78%¹¹. The most common adverse events in > 20% of patients included fatigue (43%), diarrhea (34%), nausea (30%), constipation (21%), and headache (20%).

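### Grade 4 CRS is kept out of the grade 4 suspension count and enters only as one grade 2+ CRS event, so it is never pooled with other grade 4 toxicity and has no severity-specific trigger.

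*Combined protocol and SAP*

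**What the plan says.** Section 8.0 sets three safety triggers that suspend accrual until an ad hoc committee has reviewed the data.

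- **Death.** Any single on-treatment death.
- **Grade 4 treatment-related non-hematologic toxicity.** The criterion is "If the lower limit of a 95% confidence interval does not include the possibility of this rate being < 10" (per cent), put into practice as 5/15, 7/30 or 9/42 patients. CRS is taken out of this count: "excluding CRS as this is evaluated separately". The exclusion has no grade limit.
- **CRS.** The criterion has the same form with a reference rate of 15%, put into practice as 6/15, 9/30 or 11/42. The event is that "patients have a grade 2 or higher CRS event", so grades 2, 3 and 4 each count as one patient.

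No trigger is specific to grade 3-4 or grade 4 CRS. For background, Section 4.3 reports from earlier mosunetuzumab data that "Grade 2 and 3 cytokine release syndrome was seen in 7.8% and 1.1% of patients, respectively".

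**The concern.** Evaluating CRS separately would be a full substitute if the separate rule were at least as sensitive to grade 4 events as the rule it replaces. It is not built that way. It ignores severity, it uses a higher reference rate, and its boundary is higher at every look. Appendix 14.5 shows how different the equated events are: grade 2 CRS is managed without vasopressors and with at most low-flow oxygen, while grade 4 CRS involves multiple vasopressors or positive-pressure ventilation.

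Two gaps follow. A cluster made up mainly of grade 4 CRS can meet the plan's own criterion for excess grade 4 toxicity and suspend nothing. And grade 4 events split between CRS and other toxicities sit in two separate counts, neither of which may fill. At stake is whether a non-fatal run of severe events, from the toxicity that step-up dosing is meant to limit, brings a prompt committee review while patients are still being enrolled.

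**Working it through.** **Inputs.** Boundaries and reference rates (10% and 15%) are from Section 8.0. Background grade 2-3 CRS is from Section 4.3: 7.8% + 1.1% = 8.9%. The documents give no rate for grade 4 CRS or for other grade 4 toxicity, so those rates are assumptions.

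**1. Reproduce the plan's boundaries.** The text does not state sidedness. Take the exact one-sided 95% lower limit, L = the 5% quantile of Beta(x, n − x + 1), and find the smallest x with L above the reference rate.

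| Rule | n | Boundary, L | One patient fewer, L |
|---|---|---|---|
| Grade 4, 10% | 15 | 5: 14.2% | 4: 9.7% |
| | 30 | 7: 11.5% | 6: 9.1% |
| | 42 | 9: 11.7% | 8: 9.9% |
| CRS, 15% | 15 | 6: 19.1% | 5: 14.2% |
| | 30 | 9: 16.6% | 8: 14.0% |
| | 42 | 11: 15.4% | 10: 13.5% |

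All six boundaries are reproduced.

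**2. Grade 4 CRS with no grade 2-3 CRS.** The largest counts that leave the CRS rule untouched are 6 − 1 = 5/15 and 9 − 1 = 8/30. Their lower limits are 14.2% and 14.0% one-sided (11.8% and 12.3% two-sided). All exceed the 10% criterion for grade 4 toxicity, so unstated sidedness does not matter here. The same counts of another related grade 4 non-hematologic toxicity would suspend accrual. With 7/30 grade 4 CRS, one grade 2-3 case still leaves the total at 8, below 9.

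**3. No pooling.** With different patients in each count, 5 grade 4 CRS + 4 other grade 4 = 9/15, and 8 + 6 = 14/30, trigger neither rule.

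**4. What grade 2-3 CRS does.** It fills the CRS count. The boundaries differ by 6 − 5 = 1, 9 − 7 = 2 and 11 − 9 = 2 patients, so that many grade 2-3 cases close the gap. Taking each rule alone (exact binomial, cumulative looks at 15, 30 and 42):

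| True grade 4 rate | CRS rule with 0% / 5% / 8.9% grade 2-3 CRS | Grade 4 rule, other toxicity |
|---|---|---|
| 10% | 0.5% / 5.8% / 18.7% | 4.0% |
| 20% | 23.9% / 52.3% / 73.1% | 53.0% |

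**5. Both rules together.** Model: each patient has other grade 4 toxicity with probability 5%. Independently, each has grade 4 CRS (15%), grade 2-3 CRS (varied) or neither. Accrual is suspended if either count reaches its boundary at a look. Each cell shows P(suspension) as written vs with grade 4 CRS in both counts.

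| Grade 2-3 CRS | Looks at 15, 30, 42 | Looks at 15 and 30 only |
|---|---|---|
| 0% | 6% vs 48% | 4% vs 37% |
| 5% | 24% vs 51% | 15% vs 39% |
| 8.9% | 46% vs 61% | 30% vs 46% |
| 15% | 78% vs 82% | 59% vs 66% |

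The right-hand column is the relevant one for accrual, because planned enrolment ends at 42.

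Two further cases at 8.9% grade 2-3 CRS, all three looks:
- 8% other grade 4 and 8% grade 4 CRS: 12% vs 29%. Here 1 − 0.92 × 0.92 = 15.4% of patients have a grade 4 event.
- No other grade 4 and 15% grade 4 CRS: 46% vs 48%. At this background most of the gain comes from pooling.

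**6. Cost at low rates.** With 5% other grade 4, 1% grade 4 CRS and 8% grade 2-3 CRS, exact calculation gives 0.37% vs 0.54%. A simulation of 200,000 trials gives 0.4% vs 0.6%. Either way the increase is about 0.2 percentage points.

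**The case against.** The strongest reply is that the CRS rule is broader, not looser. It counts grade 2 and 3 events, which the grade 4 rule ignores for every other toxicity, and both sets of boundaries come from the same exact limit. At the 8.9% background the CRS rule alone fires sooner than the grade 4 rule would for another toxicity (18.7% vs 4.0% at a true grade 4 rate of 10%). This stands. The largest gaps need grade 4 CRS to outnumber grades 2 and 3 combined, and nothing in the documents suggests that pattern: Section 4.3 shows mostly grade 2, and Section 4.3.1 reports only grades 1 and 2 with subcutaneous flat dosing.

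It is also true that the look at 42 cannot suspend accrual once 42 patients are enrolled, and that other safeguards exist. One death suspends accrual, Section 5.9 lists the severity of adverse reactions among its termination criteria, grade 2+ CRS is an event of special interest with rapid reporting (Section 7.2.1), and the monitoring committee reviews the study at least annually and as needed (Section 10.0). But none of these sets a numeric trigger for non-fatal grade 4 CRS, and none pools it with other grade 4 events.

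A reader might infer that life-threatening CRS always needs more patients to suspend accrual than any other grade 4 toxicity. The documents do not support that. It holds only when few grade 2-3 cases accompany the grade 4 cases; the comparator is treatment-related non-hematologic toxicity only; and hematologic grade 4 toxicity has no suspension rule at all. Nor are the boundaries miscalculated.

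**Conclusion.** The point holds in limited form. Section 8.0 has no severity-specific CRS trigger and does not pool grade 4 CRS with other grade 4 toxicity. With little grade 2-3 CRS, 5/15 or 7-8/30 patients with grade 4 CRS suspend nothing, although the same count of other related non-hematologic grade 4 toxicity would, and up to 9/15 patients could have a grade 4 event without suspension.

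The size depends on the grade 2-3 CRS rate. At 5% other grade 4 and 15% grade 4 CRS, with looks at 15 and 30, counting grade 4 CRS in both rules raises the chance of suspension by 33 points with no grade 2-3 CRS (4% to 37%), 16 points at 8.9% (30% to 46%) and 7 points at 15% (59% to 66%). These figures rest on assumed rates, on independence between CRS and other grade 4 toxicity, and on formal looks only at the stated sample sizes. The counts in steps 2 and 3 follow from the boundaries alone.

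**What to change.** In Section 8.0, delete the parenthesis that excludes CRS from the grade 4 rule. A patient with grade 4 CRS then counts toward 5/15, 7/30 or 9/42 and also toward the unchanged grade 2+ CRS boundary of 6/15, 9/30 or 11/42. One added sentence should say that treatment-related grade 4 CRS is included in the non-hematologic count, and that a patient with both grade 4 CRS and another grade 4 event counts once in it.

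No boundary changes and no new data are needed, since CRS is already graded and reported. A trigger only pauses accrual for committee review. The cost is about 0.2 percentage points more needless suspension at the low rates in step 6. If the sponsor prefers to keep the counts separate, the section should at least state how grade 4 CRS counts toward suspension and why.

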Objectives include gaining a preliminary assessment of the potential efficacy of this regimen. This will be defined as the percentage of patients that achieve a complete remission (CR) following study treatment as the primary end point, best ORR as a secondary end point. Exploratory endpoints include with PFS and OS. A simple binary proportion will be used to estimate CR and ORR, and the Kaplan-Meier method will be used to estimate PFS and OS.

Combination chemotherapy with a CD20 monoclonal antibody is highly efficacious in the treatment of indolent lymphomas, but short and long term toxicities can be seen¹⁻³. Since these studies did not all use PET-based assessments, it can be challenging to determine a reasonable

benchmark. However, recent retrospective studies would suggest the CR rate to upfront treatment is around 80%²⁵. Given potential for less toxicity with the proposed treatment, an observed CR rate that is at least as high as this benchmark would be considered promising, pending examination of other endpoints plus toxicity data. Therefore we would consider this study to be successful and merit further investigation if the observed best response as CR rate that is at least 80% among the patients treated. We propose to treat a total of 42 patients, this number not based on considerations of statistical power to reject a null hypothesis, rather on considerations of feasibility and ability to accrue. We anticipate enrolling roughly 42 patients over a 30-month period, but if the protocol is open for 36 months before 42 patients have been enrolled, consideration will be given to closing the study. If we enroll 42 patients, 34 or more complete responses would meet this benchmark. Shown in the table below is the probability of 34 or more responses among 42 patients for a variety of assumed-true CR rates. A subject will be defined as efficacy evaluable if they have had at least one response assessment. Subjects who come off study treatment for any reason prior to a response assessment will not be considered response evaluable and will not be replaced. If fewer than 42 subjects are evaluable for response after completion of the study, we will recalculate the below tables with a goal of achieving a CR as best response in at least 80% of patients.

Assumed-true CR rate	Probability of 34 or more responses among 42 patients
.65	.02
.70	.08
.75	.24
.80	.53
.85	.83
.90	.98

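### The 80% CR benchmark is set on patients treated but applied to evaluable patients, so each treated subject who is never assessed raises the reported rate and can lower the number of CRs needed

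*Combined protocol and SAP*

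**What the plan says.** Section 3.0 defines the primary objective as the "proportion of subjects who have achieved a complete response (CR) as the best response by the end of therapy", with no restriction to evaluable subjects. Section 8.0 plans the sample in the same terms ("We propose to treat a total of 42 patients") and puts the benchmark at an observed CR rate of "at least 80% among the patients treated". For 42 patients it gives this as 34 or more CRs and tabulates the probability of reaching that count.

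The same paragraph of Section 8.0 then brings in a second population. Its definition reads: "A subject will be defined as efficacy evaluable if they have had at least one response assessment". The exclusion rule comes straight after that definition and makes no distinction by cause: "Subjects who come off study treatment for any reason prior to a response assessment will not be considered response evaluable". Those excluded are not made up by new enrolment, which agrees with Section 5.8. If fewer than 42 are evaluable, the tables are to be recalculated and the 80% goal kept.

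Under Section 5.3 the first scheduled response assessment is a CT between cycle 4 day 1 and cycle 5 day 1. With 21-day cycles that is 63 to 84 days, or 9 to 12 weeks, after the first dose. Several sections ask for imaging when a subject stops early:

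- Section 5.3: "Subjects who must permanently discontinue mosunetuzumab monotherapy due to toxicity should have a response assessment".
- Section 5.7: a response assessment is described as ideal for those who stop for reasons other than progression, and the visit may be waived.
- Section 7.1.5: final-visit activities should be done at discontinuation.
- Section 7.1.6.3: a visit and imaging should follow when a subject leaves early for suspected progression or toxicity.

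**The concern.** The plan names two denominators for one decision. If every treated subject has an assessment they coincide. If one does not, a reader cannot tell from Section 8.0 which rate decides whether the study met its benchmark.

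The choice is not neutral. A subject with no response assessment cannot have a documented CR, so exclusion takes a non-CR out of the denominator and nothing out of the numerator. The exclusion applies whatever the reason for leaving, so it can reach a subject who died or stopped for toxicity before any scan. The plan has no all-treated analysis alongside to show the effect. In an uncontrolled study whose efficacy claim rests on one observed proportion, the reported rate could reach 80% while the rate among those treated does not.

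**Working it through.** **Inputs.** From Section 8.0: N = 42 treated, benchmark 80%, success count 34, and the printed probability table. The number of treated subjects never assessed (k) and the probability of leaving without an assessment (d) are not in the documents. Both are assumptions, shown over a range that starts at zero.

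**1. Reproduce the plan's figures.** The threshold is the smallest whole number at or above 0.80 × 42 = 33.6, which is 34 (34/42 = 81.0%; 33/42 = 78.6% falls short). The exact binomial probability P[Bin(42, p) ≥ 34] is:

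| True CR rate p | Plan | Recomputed |
|---|---|---|
| .65 | .02 | .019 |
| .70 | .08 | .080 |
| .75 | .24 | .243 |
| .80 | .53 | .531 |
| .85 | .83 | .831 |
| .90 | .98 | .979 |

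The printed table is correct for 42 subjects in the denominator.

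**2. The bar under the evaluable rule.** With k unassessed, n = 42 − k and the CRs needed are r = 0.80 × n rounded up. Dividing r by 42 gives the rate among those treated.

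| k | n | r | r/n (reported) | r/42 (treated) |
|---|---|---|---|---|
| 0 | 42 | 34 | 81.0% | 81.0% |
| 1 | 41 | 33 | 80.5% | 78.6% |
| 2 | 40 | 32 | 80.0% | 76.2% |
| 3 | 39 | 32 | 82.1% | 76.2% |
| 4 | 38 | 31 | 81.6% | 73.8% |
| 6 | 36 | 29 | 80.6% | 69.0% |

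The fall is stepwise because counts are whole numbers: two and three exclusions both need 32.

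**3. Chance of meeting the benchmark.** Let p be the true CR rate among all treated. Each subject independently leaves unassessed with probability d and has no documented CR, so the rate among the evaluable is p/(1 − d). Then

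P(success) = Σ over k of P[Bin(42, d) = k] × P[Bin(42 − k, p/(1 − d)) ≥ r(k)].

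For example, at p = 0.75 and d = 0.10 the evaluable rate is 0.75/0.90 = 0.833.

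| d | Expected number unassessed (42 × d) | P(success), p = 0.70 | P(success), p = 0.75 |
|---|---|---|---|
| 0% | 0 | 0.08 | 0.24 |
| 1% | 0.4 | 0.10 | 0.29 |
| 2% | 0.8 | 0.13 | 0.34 |
| 5% | 2.1 | 0.20 | 0.48 |
| 10% | 4.2 | 0.40 | 0.73 |

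If all treated subjects stay in the denominator and the unassessed count as non-CR, the first row applies whatever d is, and the printed table holds.

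**The case against.** The best defence is that few subjects will be excluded. The rule reaches only those with no assessment at all, and Sections 5.3, 5.7, 7.1.5 and 7.1.6.3 ask for imaging in most early exits. The plan expects primary progression to be rare and grade 4 non-hematologic toxicity to stay below 10%, and any on-treatment death suspends accrual for review, so an early death would not pass unnoticed. At a 1% to 2% exit probability the effect is modest. All of this stands as to size. It does not remove the inconsistency: the imaging is requested rather than assured, and cannot be obtained after death, and may not be after consent withdrawal or loss to follow-up.

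It is also fair that the recalculation is prespecified and disclosed. That makes the evaluable rule transparent, but does not reconcile it with a benchmark stated for patients treated.

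Three stronger readings are tempting and not supported:

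- A reader might infer that early deaths, toxicity withdrawals and clinical progressions are all removed as treatment failures. A subject who progresses and is scanned has an assessment and counts as non-CR. Section 5.7 also lists exits such as noncompliance and administrative reasons, which need not be treatment failures.
- A reader might infer that the two evaluability sentences contradict each other for anyone who stops mosunetuzumab for toxicity and is then scanned. Such a subject may go on to Part B, which is still study treatment, so no conflict arises there. For one who stops everything and is then scanned, the natural reading is that the assessment makes the subject evaluable. A clarifying clause is enough.
- A reader might treat 80% as a formal go/no-go test. The study is a pilot, its size is given with "this number not based on considerations of statistical power to reject a null hypothesis", success is subject to other endpoints and toxicity, and the plan calls 80% a loose benchmark. No type I error claim is made, so none is broken.

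**Conclusion.** The point holds as an inconsistency in the primary denominator with a known direction and an unknown size. The direction is arithmetic: excluding unassessed subjects can only raise the CR rate, and lower or hold the number of CRs needed. The size depends on an exit rate that the documents do not give. It is nil with no exits, small at 1% to 2% (at a true 75%, 0.29 to 0.34 against 0.24), and material at 5% to 10% (0.48 to 0.73; at a true 70%, 0.20 to 0.40 against 0.08). These probabilities assume independent exits and no documented CR among those who leave. The printed figures for 42 patients are right. Because the likely number of exclusions is small and the benchmark is informal, this is a should-fix rather than a must-fix.

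**What to change.** In Section 8.0:

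1. Define the primary denominator as all subjects who receive at least one dose of mosunetuzumab, and count a subject with no response assessment as non-CR.
2. Keep 34 of 42 as the benchmark, or at least 80% of those treated if fewer than 42 are treated.
3. Limit the recalculation sentence to the number treated.
4. Report the evaluable-only CR rate as a sensitivity analysis, and state that a scan obtained after stopping treatment makes a subject evaluable for it.

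This is a change of wording. It needs no extra patients, visits or data, and it restores the denominator that the benchmark already names. The cost is that the observed CR rate may be slightly less favourable, because some exits unrelated to treatment will count as non-CR. The change is best made before response data are reviewed.
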